For the children enrolled in active surveillance in the 6-12 weeks group, enrolment is at first administration of DTP/HepB/Hib vaccine. The home visits will take place approximately 1 week after administration of each dose of DTP/HepB/Hib vaccine (V1, V2, V3), and 6 weeks (V4) and 6 months (V5) after administration of the third dose. These visits will be followed by a visit (V6) approximately 18 months after administration of the third dose, and visits approximately 5 weeks (V7), 12 months (V8) and 24 months (V9) after V6. A last home visit (V10) will be conducted at study conclusion.

The 5-17 months group of the active surveillance will include a group of selected children identified at first administration of DTP/HepB/Hib vaccine, or first seen during hospitalisation, before first administration of DTP/HepB/Hib vaccine, and meeting the inclusion criteria for active surveillance, and a group of children aged 5 to <18 months, corresponding to a catch-up. The first visit (V1) for selected children identified at first administration of DTP/HepB/Hib vaccine will be at 6 months of age, and for children aged 5 to <18 months, corresponding to a catch-up, at time of their first encounter with study staff or approximately 1 week later. The following visits will be scheduled in a similar way as for the 6-12 weeks group.

Continuous monitoring of outpatient visits at health care facilities will be done up to the end of active follow-up (V9) for all children enrolled in the active surveillance.

Continuous monitoring of hospitalisations will be done throughout the whole study period.

CONFIDENTIAL115055 (EPI-MALARIA-002 VS AME)
Protocol Amendment 7 Final**9.1.1. Rationale for the study design**

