Visit days: 5-17 mths group (identified at first administration of DTP/HepB/Hib vaccine)		At the age of 6 mths (> 5 mths to < 7 mths)	4 wks (±3 days) post V1	4 wks (±3 days) post V2	5 wks (±5 days) post V3	6 mths (±2 wks) post V3	18 mths (±2 wks) post V3	5 wks (±5 days) post V6	12 mths (±2 wks) post V6	24 mths (±2 wks) post V6	At 5 yrs of age or study end ⁷ (±2 wks)
Visit days: 5-17 mths group (catch-up, enrolled at 5 to <18 mths of age)		First contact with study staff or 1 wk later	4 wks (±3 days) post V1	4 wks (±3 days) post V2	5 wks (±5 days) post V3	6 mths (±2 wks) post V3	18 mths (±2 wks) post V3	5 wks (±5 days) post V6	12 mths (±2 wks) post V6	24 mths (±2 wks) post V6	At 5 yrs of age or study end ⁷ (±2 wks)
Time point (Month)		M0	M1	M2	M3.5	M8	M20	M21.5	M32	M44	
Record any serious delay in developmental milestones or physical disability ³		●		●							●
Refer sick children or children with disabilities to outpatient clinic or hospital according to clinical diagnosis ⁴		●	●	●	●	●	●	●	●	●	
If death, record verbal autopsy diagnosis ⁵		●	●	●	●	●	●	●	●	●	●
Study conclusion											●

Children in 6-12 weeks group: subjects identified at first administration of DTP/HepB/Hib vaccine

Children in 5-17 months group: subjects identified at first administration of DTP/HepB/Hib vaccine or subjects 5 to <18 months (catch-up)

V= Visit; Wks = weeks; mths = months; yrs = years

● is used to indicate a study procedure that requires documentation in the individual eCRF

○ is used to indicate a study procedure that does not require documentation in the eCRF

1. Procedures at Enrolment visit may be conducted at Visit 1 for children in the 6-12 weeks group and children in the 5-17 months catch-up group.
2. All immunisations will be recorded
3. See [Annex 6](#)

CONFIDENTIAL115055 (EPI-MALARIA-002 VS AME)
Protocol Amendment 7 Final

4. See [Annex 5](#)
5. Using the INDEPTH Standard Verbal Autopsy Questionnaire [[INDEPTH](#), 2003] for children who died at home. If a site is not part of the INDEPTH, or does not have an equivalent surveillance system in place, the INDEPTH procedures for verbal autopsy might be implemented to ensure consistency across study sites.

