	
2503 Subjects recruited in the group enhanced hospitalisation surveillance (EHS) :
 
 
Subjects eliminated if no hospitalisation recorded or without hospitalisation admission dates available
 
Subjects with ICF before hospitalisation date -1 day are eliminated
 
Subjects for whom the hospitalisation admission date is before ICF and: 
 
If hospital discharge date is known then subjects with ICF signed more than 7 days after hospital discharge are eliminated.
 
If hospital discharge date is missing with ICF signed more than 7 days after hospital admission are eliminated.
 
 
 

	
2504 Subjects recruited in the group active surveillance 6-12 weeks:
 
 
Subjects without DTP or without DTP vaccine dates available eliminated
 
Subjects eliminated if ICF signed more than 10 days after 1st DTP
 
Subjects eliminated if ICF signed after first visit available
 

\*This code should be allocated only in very special occasion for fraudulent subject (e.g. lab samples received by error).

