**Table 1      Definition of at-risk period for AESI**

AESI	Risk period identified (for other licensed vaccines)*	Risk period applied
ADEM	NA	6 weeks
Encephalitis	6 weeks and 2 weeks	
Guillain-Barre Syndrome	3-5 days to 6-10 weeks	3 months
Generalized convulsive seizures	0-7 days	2 weeks
Hypotonic Hypo responsive Episode	immediately to 48h	2 weeks
Intussusception	1 to 7 days	2 weeks
Hepatic Insufficiency	1-10 days	2 weeks
Renal Insufficiency	1-10 days	2 weeks
Juvenile Chronic Arthritis	≤6 months	6 months
SJS & TEN	1-3 weeks	6 weeks
Henoch Schonlein purpura	NA	6 months
Kawasaki Disease	1 month	6 weeks
Diabetes mellitus type 1	≤6 months	6 months
Anaphylaxis	0-48 hours	2 weeks
Thrombocytopenia	12-25 days	6 weeks

\* from Table 3 of the protocol

Of note:

- The predefined list of AESI with expected at-risk period is available in the current Table 3 of the protocol,
- The at-risk period of 12 months will be used for meningitis,
- For other AEs leading to hospitalisation or death:
  - ***IR will only be computed on the 10 most frequent AEs following the grouping done by the Epidemiologists and a Physician (see section 6.9.2.2).***

- An at-risk period of 7 days and 30 days will be applied. Other risk periods may be defined with the support of the GSK Safety Physicians and the panel of experts.

**Table 2** Follow-up period definition after each dose

Risk period applied	Start	Stop earliest (i.e. date of censoring is whichever occurs first)
2 weeks	Reference date*	
 
• Date of first diagnosis of event of interest
 
• Date of death
 
• Date of next dose
 
• Date of end of risk period
 
• Date of last contact**
 
• Date of migration
 
• Date when child reaches 5 years or end of the study
 

6 weeks		
3 months		
6 Months		
12 Months		

\*Reference date: see definition detailed in section [7.2.2](#)

\*\* Date of last contact: see definition detailed in section [7.2.13](#)

Notes:

- a child may come back into the study after a certain period of lost-to follow-up. In such a case, the person-year will only consider the duration when the child was present on site (e.g. from reference date to migration date, then from immigration date to the end). To do so, a migration date will be derived using migration date from:
  - Date of migration:
    - From Study continuation
    - From Study conclusion
A return date will be derived using return date from:
  - Date of return:

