    - From Study continuation
    - From Study conclusion
In case of several migrations/returns, several migration/return dates will be computed. For such subjects, the last contact date will be computed according to migration/return dates.
In case of any inconsistencies regarding the migration/return dates, the return will not be considered and the subject will be censored at the first migration date.
- If the ICF is signed after the first reference date, the individual follow-up period will be computed as the difference +1 between the follow-up end date and the ICF date. The follow-up end date remains the same as for subjects with ICF signed before the first reference date.

When AESI will be grouped, in case of multiple cases for a subject, only the first event will be considered in this analysis.

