### 6.10.6. Febrile convulsions

- Descriptive analysis

Data about febrile convolution (definition in Section 7.2.7) within 7 days (day of vaccination and 6 subsequent days) and within 30 days (day of vaccination and 29 subsequent days) of EPI vaccine will be presented. **Separate listings** will include the diagnostic certainty level as defined in Job Aid, the duration of seizures in minutes when applicable, the time from vaccination and number of seizures.

- The IR of febrile convulsions will be computed as described in section 6.9.3.2. Of note, two at-risk periods will be considered: 0-6 and 7-29 days.

*Of note, risk period might be revised if deemed necessary at the time of the analysis.*

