#### 7.2.2. Reference date

The reference date is defined as:

- For the 6-12W study group:
  - Date of vaccination for the DTP/HepB/Hib vaccine dose received
  - Virtual vaccination: virtual dose 4 one week before Visit 6 (i.e. Month 20) mimicking study schedule in the subsequent EPI-MAL-003
- For the 5-17M study group (as they do not follow study visits according to EPI vaccine administrations schedule) in order to mimic study procedures in the subsequent EPI-MAL-003, the virtual vaccinations are:
  - Virtual dose 1: one week before first visit (i.e. Month 0)

- Virtual dose 2: one week before Visit 2 (i.e. Month 1)
- Virtual dose 3: one week before Visit 3 (i.e. Month 2)
- Virtual dose 4: one week before Visit 6 (i.e. Month 20).

Note: For the 5-17M 1st DTP group, the first visit (V1) will be at the age of approximately 6 months. In case an event occurred after ICF signature but before V1, the event will not be included in the computation of IR following EPI vaccine or virtual vaccination, but the event will be included in the computation of IR in children <5 years.

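### The SAP's late-consent rule gives zero or negative person-time in the 7-day dose-1 windows, which shrinks the denominator and inflates those rates

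*SAP*

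**What the plan says.** **When consent can occur.** The Figure 1 legend (Protocol 9.1) says that for the 6-12 weeks group "enrolment is at first administration of DTP/HepB/Hib vaccine". Footnote 1 to Protocol Table 4 adds an alternative: "Procedures at Enrolment visit may be conducted at Visit 1 for children in the 6-12 weeks group". Table 4 sets Visit 1 at one week ±3 days after the first DTP dose, that is, days 4 to 10.

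**Who stays in the analysis.** SAP 5.2, code 2504, has two consent limits for this group: "Subjects eliminated if ICF signed more than 10 days after" the first DTP dose, and "Subjects eliminated if ICF signed after first visit available". A child who consents at a Visit 1 held on days 7-10 passes both.

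**When the clock starts.** SAP 7.2.2 defines the reference date for this group as "Date of vaccination for the DTP/HepB/Hib vaccine dose received". For the 5-17 months group, virtual dose 1 is one week before Visit 1.

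**Which windows are short.** For other AE leading to hospitalisation or death (co-primary), SAP 6.9.3.2 says "An at-risk period of 7 days and 30 days will be applied". For febrile convulsions (secondary), SAP 6.10.6 says "two at-risk periods will be considered: 0-6 and 7-29 days". No AESI window is shorter than 2 weeks.

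**How late consent is handled.** The notes after SAP Table 2 state that "the individual follow-up period will be computed as the difference +1 between the follow-up end date and the ICF date" and leave the end date as it would be for a child who consented earlier. SAP 6.9.3.2 builds total person-years by adding up the individual periods. Rates are presented for doses 1-3 combined and for doses 1-3 plus virtual dose 4.

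**The concern.** Leaving out days before consent is sound delayed-entry practice. The rule, however, covers only consent that falls inside the window. If consent comes after the window has closed, the subtraction gives zero or a negative number, and the sum over children then removes days validly observed after doses 2 and 3 or in other children.

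Two gaps add to this. SAP Table 2 has no 7-day or 30-day row, so the last day of the 7-day window is written only for febrile convulsions. And nothing removes a 6-12 weeks event with onset between the first DTP dose and consent. The rule on events outside the at-risk period does not help, because Table 2 starts that period at the reference date and not at consent. SAP 7.2.2 gives an explicit exclusion before Visit 1 for the 5-17 months children enrolled at first DTP, but no equivalent for this group.

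At stake are one co-primary rate and the febrile convulsion rate. Rates following vaccination are shown by site, so any site difference in when consent is taken would shift them for a reason unrelated to risk.

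**Working it through.** **The plan's own figures reproduce.** Protocol Table 6, 2-week window: 10,000 × 4 doses × 2/52 = 1538.46 person-years; one event gives 65.0 per 100,000, exact Poisson interval 1.6 to 362.2, as printed. The 6-week row: 10,000 × (2/12 + 2 × 6/52) = 3974.36, also as printed. The SAP worked examples give 7 + 14 + 10 = 31 days, 28 + 14 + 34 = 76 days, and 76 + 42 = 118 days. All of these assume follow-up from dose 1, and none covers a 7-day window or late consent.

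**Dose-1 person-time by consent day d** (formula: end day − d + 1)

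| Window end | d=4 | 5 | 6 | 7 | 8 | 9 | 10 |
|---|---|---|---|---|---|---|---|
| day 6 (days 0-6) | 3 | 2 | 1 | 0 | −1 | −2 | −3 |
| dose + 7 | 4 | 3 | 2 | 1 | 0 | −1 | −2 |
| day 13 (2 weeks) | 10 | 9 | 8 | 7 | 6 | 5 | 4 |
| day 29 (30 days) | 26 | 25 | 24 | 23 | 22 | 21 | 20 |

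Only the 7-day window goes to zero or below by this route. One child consenting on day 10 has −3 + 7 + 7 = 11 days for the primary schedule, against 0 + 7 + 7 = 14 actually observed.

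**Effect on the rate.** Assumption: a share s consents at Visit 1, spread evenly over days 4-10, and the rest consent on the day of the dose.

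- End day 6: the late consenters average (3+2+1+0−1−2−3)/7 = 0 days as written, and (3+2+1)/7 = 0.857 with a floor at zero. Primary schedule per child: 14 + 7(1−s) as written, against 14 + 7(1−s) + 0.857s.
- End at dose + 7: the averages are 7/7 = 1 and 10/7 = 1.429.

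| Share at Visit 1 | Rate as written ÷ floored, end day 6 | Same, end dose + 7 |
|---|---|---|
| 10% | 20.386/20.3 = 1.004 | 20.443/20.4 = 1.002 |
| 50% | 17.929/17.5 = 1.024 | 18.214/18.0 = 1.012 |
| 100% | 14.857/14.0 = 1.061 | 15.429/15.0 = 1.029 |

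For 10,000 children with end day 6, the 50% row is 479.1 against 490.9 person-years. If every child consented, evenly, on days 7-10, the ratios are 14/12.5 = 1.12 (end day 6) and 14.25/13.5 = 1.056 (dose + 7). Adding virtual dose 4 reduces the effect: at 100% over days 4-10 with end day 6, 21.857/21 = 1.041.

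**Events before consent.** Table 2 stops follow-up at first diagnosis. Onset on day 2 with consent on day 7 gives 2 − 7 + 1 = −4 days and, if the event is counted, one event. This can happen with any window length.

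**Catch-up children (5-17 months).** Consent at Visit 1 is day 7 after virtual dose 1, so the 7-day dose-1 window yields 0 days (end day 6) or 1 day (dose + 7).

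**Day count.** In the first SAP example an event 7 days after a dose contributes 7 days. The +1 convention would give 7 − 0 + 1 = 8.

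**The case against.** The strongest reply is that this is a small gap in wording. A programmer would probably set a floor at zero, and SAP 7.2 says that programming specifications, which are not public, support the SAP. The finding can therefore be stated only of the SAP text. The size is modest, and the share consenting at Visit 1 is unknown. Protocol 9.2.7.1.8 records facility contacts between enrolment and Visit 1, so events before consent may seldom be captured. The 6-12 weeks group is not carried into EPI-MAL-003, and its dose-1 window follows DTP, not RTS,S. All of this stands and limits the importance. It does not make the formula right, and the catch-up children are part of the 5-17 months group, which is carried forward.

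The Figure 1 legend and Table 4 do not conflict: Protocol 9.2.7.1 also allows enrolment about a week later.

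A reader might infer that zero or negative person-time dilutes the short-window rates. The documents do not support that. Negative days shrink the denominator and raise the rate, and zero days leave it unchanged.

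A separate reading is that AESI with an identified period of about a week or less, analysed on 2 weeks, are underestimated because a child consenting on day 7 contributes only days 7-13. If all risk lay in days 0-6 and events before consent were not counted, the rate ratio would be (14/35)/(21/42) = 0.80 with every child consenting on day 7, and (35/77)/(21/42) = 0.91 with half. If those events were counted, it would be (21/35)/(21/42) = 1.20. The SAP says neither, and the risk pattern is hypothetical, so no direction can be claimed. The 2-week minimum is a protocol choice, and time to onset will be described.

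**Conclusion.** The rule is wrong as written. Consent on days 7-10 is within plan, and the stated formula then gives 0 to −3 days (window ending on day 6) or 1 to −2 days (ending at dose + 7) for the 7-day dose-1 windows. The direct effect is to inflate the 7-day primary-schedule rates by about 0.2% to 6% over assumed Visit 1 shares of 10% to 100%, and by about 12% if all children consent evenly over days 7-10. These sizes rest on the assumed share and spread of consent days, which the documents do not give.

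The 2-week and longer windows stay positive unless follow-up stops before consent, for example at an event diagnosed before consent. Whether such events count is not stated. The case for correcting this rests on negative person-time being invalid at any size, not on a large bias.

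**What to change.** In SAP 6.9.3.2, for all active-surveillance groups:

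- Start each dose window at the later of the reference date and the consent date.
- If consent falls after the window end, leave that dose window out of both numerator and denominator. Person-time is then zero, never negative.
- Count only events with onset on or after consent.
- Add 7-day and 30-day rows to Table 2 with a fixed last day (for example days 0-6 and 0-29), and use one day-count convention throughout, including the worked examples.
- Report by site the number of children and person-days contributing to dose-1 days 0-6, so that thin early coverage is visible for short-latency AESI on the 2-week window.

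Restricting dose 1 to children who consented by the day of DTP1 is not needed. It would discard validly observed days (consent on day 1 would lose days 1-6) and has no meaning for catch-up children.

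The cost is SAP wording and programming, with slightly fewer countable early events and slightly wider intervals.

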## Management of the at-risk period

- Events occurring outside of the at risk period (before or after) will be censored for the main analysis. The distribution of the Time to Onset (TTO) of events after EPI vaccine or virtual dose will be described, and additional at-risk periods may be considered based on the results as sensitivity analyses.

- In case an AESI had several at-risk periods, the longest will be considered for analysis:

Example: Guillain-Barré Syndrome: expected at-risk period from 3-5 days to 6-10 weeks, as a consequence an at-risk period of 3 months will be applied

[figure not shown]
- In the same way, for the analysis of grouped AESI with different at-risk periods, the longest will be considered:

Example: Encephalitis (2-6 weeks at risk period) and Generalised convulsive seizure (0-7 days at risk period) as a consequence an at-risk period of 6 weeks will be applied

- In case an AESI occurs after the specified at-risk period, it will be censored at the time-point (e.g.: 2 weeks in the example below) and new at-risk period could be discussed.

### First example of AESI with 2 weeks at-risk period:

The following diagram represent a theoretical scenario for one subject presenting a first AESI 7 days after the first dose, a second AESI 9 days after the first dose, a third AESI 10 days after the third dose and a fourth AESI 16 days after the fourth dose.

[figure not shown]

Of note, in case of recurrence of the event after a specified dose, the follow-up will stop at first occurrence.

When computing incidence rate for the primary schedule, the follow-up period corresponding to each dose should be summed. In our example: the follow-up period to consider for the primary schedule is: 7 days + 14 days + 10 days and two events will be considered (the first one after each dose).

### Second example of AESI with 6 weeks at-risk period:

The following diagram represent a theoretical scenario for one subject presenting a first AESI 6 weeks (42 days) after the first dose corresponding also to 2 weeks (14 days) after the second dose, a second AESI 5 weeks (34 days) after the third dose and a third AESI more than 6 weeks (45 days) after the fourth dose.

As mentioned earlier, the at-risk period will follow any dose, with a censoring of subjects when they receive the following dose. Then in our example the follow-up period to consider for:

- First dose: 28 days with no event\*
- Second dose: 14 days with one event
- Third dose: 34 days with one event
- Primary schedule: 28 days + 14 days + 34 days with two events considered.
- Virtual fourth dose: censoring at 6 weeks
- Secondary schedule: 28 days + 14 days + 34 days + 42 days with two events.

*\* Note: In case no event occurred between doses, the exact number of days between the two doses will be considered to compute the follow-up period.*

### Incidence rates over all study sites

[figure not shown]
The crude incidence rate (unadjusted) over all sites will be computed. If relevant, the adjusted overall incidence rate will be computed considering the study sites as clusters.

#### 6.9.3.3. Incidence in children < 5 years

The IR of each and any AESI, of each and any other AE leading to hospitalisation or death (classified by the MedDRA SOC and PT level) and of aetiology confirmed meningitis will be estimated in all children < 5 years per 100,000 person per year. A 95% CI will be computed per year and overall using an exact method for a Poisson variable.

The numerator will be the number of cases of specified events (i.e. AESI) during the study period (in both AS and EHS grouped) and the denominator will be the person-years contribution of children in all communities < 5 years of age. The denominator will be computed using the census data. A census done at least once a year will provide the total number of children under 5 years.

For example, considering 5 census done between January 2015 and January 2017, a first subject recruited in March 2015 and a last subject recruited in April 2017:

The person-year (PY) will be computed as:

$$PY = N1 \cdot \text{Period1} + N2 \cdot \text{Period2} + N3 \cdot \text{Period3} + N4 \cdot \text{Period4} + N5 \cdot \text{Period5}$$

Contrary to the computation of IR following EPI vaccine or virtual vaccination where only the first event is counted in the numerator, for IR in children < 5 years, in case a subject had more than once the same AESI, all events will be counted in the numerator.

Confidence intervals [CI] will be computed using the exact method [[Clopper, 1934](#)].

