9.7.5. Analysis of co-primary objectives**9.7.5.1. Analysis population**

The population will include the subjects from the active surveillance of the EPI-MAL-002 study.

A secondary population will include the subjects from the active and enhanced hospitalisation surveillance of the EPI-MAL-002 study, computing incidence for all children < 5 years.

9.7.5.2. Statistical approach**9.7.5.2.1. Incidence of AESI, and other AE leading to hospitalisation or death**

The incidence rate of each AESI and other AE leading to hospitalisation or death will be calculated by dividing the number of subjects reporting at least one event over the follow-up period by the total person-time. A 95% CI will be computed using an exact method for a Poisson variable. The at-risk period will follow any dose, with a censoring of subjects when they receive the following dose. The minimum at-risk period for the analyses is 2 weeks. All AESI expected to occur between 0 day and 13 days following

CONFIDENTIAL

115055 (EPI-MALARIA-002 VS AME)
Protocol Amendment 7 Final

dose administration (see [Table 3](#)) will be analysed with an at-risk period of 2 weeks. The at-risk period of 6 weeks will be used for AESI expecting to occur between 14 days and 6 weeks. Finally, at-risk periods of 3 months, and 6 months will be for the AESI expected to occur between 6 weeks and 3 months, and between 3 months and 6 months, respectively. For other AE leading to hospitalisation or death the at-risk period for the analyses will be defined with the support of the GSK safety physicians and the panel of experts. In addition, the distribution of the Time-to-Onset of events after vaccination will be described, and additional at-risk periods will be considered based on the results as sensitivity analyses.

The person-time for an event of interest (e.g. juvenile chronic arthritis) will be calculated as the time between the reference date (date of first administration of DTP/HepB/Hib vaccine or date of first virtual vaccination, corresponding to the week before first visit) and the end of the at-risk period or the earliest of the followings:

- Date of first diagnosis of event of interest (e.g. first episode of juvenile chronic arthritis).
- Date of end of study period.
- Date of enrolment in EPI-MAL-003 (when applicable).
- Date when child reaches 5 years.
- Date of last contact (Lost-to follow-up).
- Date of death.

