#### **6.10.5. Cause of hospitalisation (including AESI, other AE, meningitis and malaria) and death**

Causes of hospitalisation (including AESI, other AE, classified by MedDRA SOC and PT level as well as meningitis and malaria) will be analysed grouped as follows:

- Hospitalisations (all causes)
- Hospitalisation for malaria (including *P. falciparum* malaria)
- Hospitalisation for *P. falciparum* malaria

In the same way, descriptive analysis of causes of death classified by MedDRA will be done overall and by gender grouped as follows:

- Deaths – all cause
- Malaria attributed deaths (including *P. falciparum* malaria)
- *P. falciparum* malaria attributed deaths
- Deaths attributed to an AESI or other AE (i.e. other than meningitis, AESI, malaria)

Descriptive analysis of the cause of hospitalisation (overall) and death (overall and by gender) will consist in computing the number of cases, person-year per 100,000 and IR (with 95% CI).

IR of all cause of hospitalisation and death will be computed following EPI vaccine or virtual vaccination (at risk period of 12 months) as described in section [6.9.3.2](#) and for children < 5 years as described in section [6.9.3.3](#). Of note, death IR per gender in children < 5 years will be computed after the first year of recruitment. Indeed, census per gender will be available after the application on field on the Protocol Amendment 4.

Note that malaria subtype will be defined using outpatient and hospitalisation visits. In case of death occurring at home malaria subtype may be unknown.

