### **7.2.8. Management of consecutive visits and/or hospitalisations**

#### **7.2.8.1. AESI, Meningitis and other AE**

For cases reported at hospital, events in one subject with the same preferred term and with the same onset date or onset date + 1 day will be considered as the same event. In such case, they will contribute to several hospitalisations and one event.

*Remarks:*

1. For other AE leading to hospitalisation or death, if the AE is not the primary diagnosis the hospital admission date will be considered (indeed, the onset date is only available for primary diagnosis).
2. For meningitis a worst case allocation is applicable. In case two or more hospitalisations occurred for different protocol definitions of meningitis with the same onset date or onset date + 1, the event considered will be the worst according to the following order (starting from worst):
  - Bacterial confirmed meningitis / Aetiology confirmed meningitis

- Probable meningitis
- Clinically suspected meningitis
- Suspected meningitis without diagnosis done by the site yet (applicable for progress report)
- Suspected meningitis ruled out afterward

3. This rule is applicable if their onset dates are complete.

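### The under-5 AESI rates count every repeat event in a child but keep an exact Poisson interval, so the intervals are too narrow wherever an AESI recurs

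*SAP*

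**What the plan says.** SAP 6.9.3.3 covers each and any AESI, each and any other AE leading to hospitalisation or death, and aetiology-confirmed meningitis. The numerator is a count of cases pooled over active and enhanced hospitalisation surveillance; the denominator is census person-years. On the interval: "A 95% CI will be computed per year and overall using an exact method for a Poisson variable". On repeats, in explicit contrast to the post-vaccination rates: "in case a subject had more than once the same AESI, all events will be counted in the numerator". The section later adds "Confidence intervals [CI] will be computed using the exact method", citing the binomial (Clopper) reference.

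SAP 6.10.5 brings in hospitalisation. It begins "IR of all cause of hospitalisation and death will be computed following EPI vaccine or virtual vaccination", and the same sentence goes on to apply 6.9.3.3 for children under 5. SAP Table 5 marks under-5 incidence for all-cause and malaria hospitalisation and for other AE in aggregated form only.

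SAP 7.2.8.1 merges two records only when they share a preferred term and their onsets are at most one day apart. A merged event still counts as several hospitalisations. For undated secondary diagnoses, "For other AE leading to hospitalisation or death, if the AE is not the primary diagnosis the hospital admission date will be considered".

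Protocol 9.7.5.2.1 defines the AESI and other-AE rate by "dividing the number of subjects reporting at least one event over the follow-up period by the total person-time", also with an exact Poisson interval.

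**The concern.** The exact Poisson interval suits a count of children with at least one event, because each child adds at most one. Once repeats are counted, events cluster within children and the count varies more than a Poisson variable with the same mean.

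The SAP has two devices that might have dealt with this, and neither reaches these rates. The dispersion parameter and negative binomial steps in 7.5.1.2 belong to the risk-factor regressions. The cluster-adjusted overall rate at the end of 6.9.3.2 uses study sites as clusters, not children, and applies only if relevant.

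The study exists to supply background rates for EPI-MAL-003. An interval that is too narrow overstates how well the background is known.

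**Working it through.** **The plan's own figure.** Protocol Table 7 assumes a birth cohort of 11,500 and 2 years: 11,500 x 5 x 2 = 115,000 person-years. Exact Poisson limits for n events are chi2(0.025; 2n)/2 and chi2(0.975; 2n+2)/2, divided by person-years. For 25 events this gives 21.7 [14.1, 32.1] per 100,000, as printed; the rows for 1, 5 and 50 events also reproduce. Clopper-Pearson limits on 115,000 agree to one decimal for 25 events, so the second exact method named in 6.9.3.3 is not the problem.

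**Variance with repeats.** Let the number of affected children be Poisson and let child i have y_i events. The variance of the total divided by its mean is phi = E[y^2]/E[y]. The exact interval assumes phi = 1. If a fraction q of affected children have two events and the rest one, E[y] = 1 + q and E[y^2] = (1 - q) + 4q = 1 + 3q, so phi = (1 + 3q)/(1 + q).

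**Coverage.** The documents give no q, so the values below are assumptions. Simulation used 200,000 replicates per cell. The large-sample value is 2*Phi(1.96/sqrt(phi)) - 1, where Phi is the normal distribution function.

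| q | phi | large-sample | 20 affected | 50 affected | 200 affected |
|---|---|---|---|---|---|
| 0.1 | 1.18 | 93% | 95.2% | 93.8% | 93.7% |
| 0.2 | 1.33 | 91% | 92.4% | 92.7% | 91.8% |
| 0.3 | 1.46 | 90% | 89.6% | 90.0% | 90.0% |
| 0.5 | 1.67 | 87% | 88.1% | 87.0% | 87.2% |

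With q = 0, coverage is 95.2-95.7%. More events do not cure the shortfall.

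**A second recurrence model.** Let r be the assumed chance that an event is followed by another in the same child, so phi = (1 + r)/(1 - r). At 50 expected events, coverage is 92.7%, 89.5% and 85.5% for r = 0.1, 0.2 and 0.3. At 5,000 it is 92.5%, 89.1% and 84.9%.

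**Small counts.** At 5 expected events the exact method starts at 98.0% and falls to 96.5% (r = 0.1), 94.5% (r = 0.2) and 91.7% (r = 0.3). Its conservatism absorbs mild recurrence.

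**Effect on the printed interval.** Suppose the 25 events come from 20 children, 5 of them with two (illustrative). Sum of y_i = 25; sum of y_i squared = 15 + 5 x 4 = 35; phi = 35/25 = 1.4; effective count 25/1.4 = 17.86. Exact limits on 17.86, times 1.4, over 115,000 give [12.9, 34.4] in place of [14.1, 32.1].

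**The case against.** The strongest reply concerns scope, and much of it stands. The all-events sentence names AESI only. For hospitalisation and other AE, repeat counting has to be inferred from the case-count numerator, the cross-reference in 6.10.5 and the merging rule in 7.2.8.1. SAP Table 4, in a different analysis, counts children hospitalised. A reader might infer that hospitalisation and any other AE are certainly affected and are the worst cases. The text does not establish that: Table 5 drops the under-5 other-AE rates by SOC and PT in favour of medical groups, so diagnoses from one admission that fall in different groups would not meet in one rate.

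A reader might also infer that the SAP abandoned a first-event rule in the protocol for these rates. The protocol's subject-based definition is general, but its own under-5 precision table already pairs numbers of detected events with exact Poisson limits. The contrast does not carry the point and is not needed for it. Nor are the post-vaccination rates wholly free of repeats: the worked examples in SAP 6.9.3.2 count two events from one child after different doses.

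SAP 6.9.3.3 defers the method of computing incidence to a technical annex that was not supplied. The annex might add a correction, but the SAP text names the interval, and that is what stands for now.

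Finally, the practical loss can be small. With an assumed 5,000 events in 115,000 person-years, the exact limits are 4228 to 4470 per 100,000 (about 2.8% either side). At r = 0.2 they become 4202 to 4498 (about 3.4%).

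**Conclusion.** The point holds for AESI. As written, SAP 6.9.3.3 attaches an interval that assumes independent events to a count that includes repeats, and nothing else in the SAP repairs it. The endpoints most exposed are generalised convulsive seizure and any AESI. For under-5 hospitalisation and the aggregated other-AE groups the point is conditional on events or admissions being counted.

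The size rests on assumed recurrence: at 20 or more affected children, coverage is about 93-95%, 91-93%, 90% and 87-88% when 10%, 20%, 30% and 50% of affected children have two events. There is no effect on deaths, on one-time diseases such as type 1 diabetes, or on any point estimate, and little at about 5 events with mild recurrence.

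A reader might infer that a later comparison with EPI-MAL-003 is thereby invalid. The documents do not support that: they place the before-after models in EPI-MAL-003 and plan no test of later rates against these intervals.

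**What to change.** In SAP 6.9.3.3, for all under-5 rates, per year and overall:

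- After the merging in 7.2.8.1, let y_i be the events of child i in the period, n = sum of y_i, and phi = (sum of y_i squared)/n over children with events (phi = 1 if n = 0).
- Take exact Poisson limits on n/phi: chi2(0.025; 2n/phi)/2 and chi2(0.975; 2n/phi + 2)/2. Multiply by phi and divide by census person-years.
- State whether the hospitalisation and other-AE numerators are events or children.
- Name one exact method for the section.

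When no child repeats, phi = 1 and this is the planned interval, so no data-dependent switch is needed. In the simulation it covered 94-98% at 5 affected children and 95-96% at 20, 50 and 200. It did not raise the lower limit at any count from 1 to 199 with phi up to 5. A log-scale interval with SE sqrt(sum of y_i squared)/n is less suitable at small counts: for 5 events in 4 children (one with two), it moves the lower limit on the count up from 1.62 to 5 x exp(-1.96 x sqrt(7)/5) = 1.77, whereas the effective-count method gives 1.23.

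The cost is a short SAP addition and a few lines of code on per-child counts already held. Nothing is needed on children who were never enrolled. Intervals become somewhat wider where repeats occur, by a factor of roughly sqrt(phi): 1.15 at q = 0.2 and 1.29 at q = 0.5.
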